## ABILITY OF PARTIAL INVERSE AGONIST, IOMAZENIL, TO BLOCK ETHANOL EFFECTS IN HUMANS

Principal Investigator: [name] [name]

Objective: The main objective of this study is to evaluate whether iomazenil can attenuate the affective and cognitive effects of alcohol.

Background: The pathological use of alcohol is a major public health challenge facing VHA. Among soldiers returning from Iraq and Afghanistan, alcoholism is one of the most common initial psychiatric disorders. There is a need to develop effective treatments for alcohol intoxication and alcoholism. The stimulation of extrasynaptic GABAA receptors by ethanol contributes substantially to its effects at doses associated with human intoxication. Therefore, drugs that could block ethanol actions at GABAA receptors might play a unique role in the treatment of alcohol intoxication and alcoholism. Preclinical studies suggest that benzodiazepine inverse agonists, but not benzodiazepine antagonists, attenuate the effects of ethanol on many levels.

They attenuate ethanol-stimulated Cl influx thereby affecting the rewarding, sedating, ataxic, and amnestic effects of ethanol, the discriminative stimulus effects of ethanol, operant behavior motivated by ethanol and ethanol self- administration. However, this has not yet been shown in humans. This project is evaluating the benzodiazepine partial inverse agonist, iomazenil, as an agent that could reverse alcohol's effects on subjective intoxication, alcohol's effects on driving using a driving simulator and on measures of electrophysiology in the laboratory in healthy subjects.

Research Methodology: We hypothesize that: the GABAA benzodiazepine partial inverse agonist, iomazenil, will attenuate several measures of ethanol intoxication in healthy human subjects. In a double-blind, placebo-controlled fashion, counterbalanced, within-subjects design, participants will receive an intravenous (IV) infusion of placebo or active ethanol (target BrAc=100mg%) followed by placebo or active iomazenil (3.7 μg/kg) administered intravenously via a separate IV. Subjects will undergo four test days. Subjects will receive the following drug combinations: (1) active ethanol and active iomazenil; (2) active ethanol and placebo iomazenil; (3) placebo ethanol and active iomazenil; and (4) placebo ethanol and placebo iomazenil. Measures of intoxication will be collected before, and several times during and after drug administration. Automobile driving will be assessed using a driving simulator. Cognitive function will be assessed using the visual novelty oddball paradigm. EEG will be recorded during the driving simulator and novelty oddball tasks, allowing for the analysis of ERP components related to making errors (error-related negativity, ERN; driving simulator) and target (P3b)

Innovation and Impact: Although inverse agonists have been shown to attenuate several aspects of ethanol in animals, this has not yet been demonstrated in humans. The innovative elements of the study are:1) the use of the only BZ inverse agonist probe available for use in humans – one that was developed at this center and to our knowledge is not available elsewhere for use at pharmacological doses, 2) the use of event- related potential and event-related oscillations, 3) the use of simulated driving, a functional measure of ethanol effects, and driving error-related potentials, 4) the use of eyeblink conditioning as a biomarker of alcohol's effects on cerebellar function. This study may provide insights into the neurobiology through which iomazenil attenuates features of ethanol intoxication in humans. In so doing, this project may help to advance the exploration of benzodiazepine inverse agonists as ethanol "antidotes" and possible treatments for pathological alcohol use. Characterizing the interplay of iomazenil-ethanol interactions on several overlapping measures will contribute to the rational development of agents similar to iomazenil as antidotes or pharmacotherapies for alcoholism.

Ability of Partial Inverse Agonist, Iomazenil,
to Block Ethanol Effects in Humans

NCT01590277

June 10, 2022

ABILITY OF PARTIAL INVERSE AGONIST, IOMAZENIL, TO BLOCK ETHANOL EFFECTS IN HUMANS

Principal Investigator: [name] [name]

Statistical Analysis Plan: All data will be transcribed onto respective teleforms, checked for completeness and clarity. Continuous variables will be checked for normality using normal probability plots and Kolmogorov- Smirnov statistics. Transformations will be applied if necessary. A criterion of $P < 0.05$ will be used throughout to determine statistical significance. In the mixed models described below, the correlation between repeated measures on an individual will be modeled using random effects and/or structured variance-covariance matrices. The best-fitting variance-covariance structure will be determined by information criterion. The mixed-effects approach is advantageous in that it is unaffected by randomly missing data and allows greater flexibility in modeling the correlation structure of repeated-measures data. We will test for order effects, although any such effects should be greatly minimized with the inclusion of the baseline session. All tests will be two-sided and considered statistically significant at $\alpha=.05$. Significance levels for secondary comparisons will be adjusted for multiple tests using the Bonferroni correction, basing the adjustment on the number of conceptually related statistical tests within each hypothesis.

To determine whether iomazenil, attenuates the “buzzed” feeling state of ethanol intoxication in healthy human subjects. We expect that the behavioral data will not conform to normality as in our previous studies. Therefore, a nonparametric analysis for repeated measures data will be conducted with ethanol (active or placebo), iomazenil (active or placebo) and time as within-subject factors. The analysis will be performed by rank transforming the data, then fitting a mixed-effects model with an unstructured variance-covariance matrix using PROC MIXED in SAS (SAS Institute Inc, Cary, NC), and finally adjusting the P values for the analysis of variance-type statistics (ATS). One of the advantages of this approach is that it uses all available data on each subject including dropouts. If the 3-way interaction among ethanol, iomazenil, and time are significant, contrasts for testing interactions between iomazenil and ethanol will be performed at each time point. For the points where significant interactions are observed, the simple effects of ethanol, and iomazenil will be tested to determine the nature of the interaction. Bonferroni corrections will be applied for multiple analyses within, but not across, domains.

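### The model for the four-day crossover has no test-day term, so drift between days would enter the error of the per-time-point contrasts and simple effects; adding the term is nearly free.

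*SAP*

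**What the plan says.** The protocol's Research Methodology paragraph describes a "double-blind, placebo-controlled fashion, counterbalanced, within-subjects design". It adds "Subjects will undergo four test days", one for each of the four drug combinations, and "Measures of intoxication will be collected before, and several times during and after drug administration".

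The general paragraph of the SAP states: "We will test for order effects, although any such effects should be greatly minimized with the inclusion of the baseline session". The phrase baseline session occurs only there, and neither document describes such a session.

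The SAP paragraph on the buzzed feeling state contains the only model that is written out. Its factors are "ethanol (active or placebo), iomazenil (active or placebo) and time as within-subject factors", fitted to ranked data with an unstructured covariance matrix. The testing sequence follows: "If the 3-way interaction among ethanol, iomazenil, and time are significant, contrasts for testing interactions between iomazenil and ethanol will be performed", separately by occasion, and where that interaction is significant "the simple effects of ethanol, and iomazenil will be tested to determine the nature of the interaction". Because the contrasts are made at each time point, time means occasion within a day and cannot stand for test day. Subjects who drop out stay in the analysis.

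**The concern.** In a four-period crossover, responses can change from day to day whatever was given, for example through familiarity with the setting or the scales. Counterbalancing spreads such drift over the four conditions but does not remove it from the data. A model with a day effect takes it out. A model without one leaves it in the error that the treatment contrasts are judged against.

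The results at stake are the follow-up ones: the ethanol by iomazenil contrasts at each time point and the simple effects. These show when and how iomazenil attenuates ethanol. The plan also applies further correction ("Bonferroni corrections will be applied for multiple analyses within, but not across, domains"), so precision lost here is not regained elsewhere. The SAP takes order effects seriously enough to test for them, but nothing in the written model carries the result.

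**Working it through.** The documents state no sample size, SD, power, drift or order scheme, so there is no planned figure to reproduce. The size of the effect follows from the design, given an assumed drift.

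**Inputs.** From the documents: four test days, a 2 × 2 set of conditions, counterbalanced order, two-sided α of 0.05. Assumed: linear drift totalling D within-subject SDs from day 1 to day 4, constant within each day; within-subject variance 1; raw rather than rank scale.

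**1. Day offset in one subject's contrast.** The day scores are −D/2, −D/6, D/6, D/2. The interaction contrast adds two conditions and subtracts the other two, so its variance is 4. Its offset depends on which two days carry the added conditions:
- days 1, 2 or days 3, 4: ±4D/3
- days 1, 3 or days 2, 4: ±2D/3
- days 1, 4 or days 2, 3: 0

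Over balanced orders the offsets average to zero, so there is no bias. Their mean square adds to the estimated error.

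**2. Inflation, 1 + c × D².**
- Contrast, all 24 orders: (16/9 + 4/9 + 0)/3 = 20/27; divided by 4, c = 0.185.
- Contrast, four-sequence Williams layout, non-cancelling labelling: (16/9 + 4/9)/2 = 10/9; divided by 4, c = 0.278.
- Contrast, Williams layout, cancelling labelling: every offset is 0, so c = 0.
- Simple effect (variance 2), all 24 orders: (3 × 1/9 + 2 × 4/9 + 1 × 1)/6 = 0.370; divided by 2, c = 0.185. In Williams layouts c is 0.139 or 0.278, never 0.

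**3. Power.** With orders balanced by design, drift inflates the estimated standard error but not the true one. A contrast with 80% power when there is no drift therefore has power Φ(2.80 − 1.96√v), where v = 1 + cD² and 2.80 = 1.96 + 0.84. Its type I error is 2[1 − Φ(1.96√v)].

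| D | v (c = 0.185) | power | type I | v (c = 0.278) | power | type I |
|---|---|---|---|---|---|---|
| 0.5 | 1.046 | 79% | 4.5% | 1.069 | 78% | 4.3% |
| 1 | 1.185 | 75% | 3.3% | 1.278 | 72% | 2.7% |
| 2 | 1.741 | 59% | 1.0% | 2.111 | 48% | 0.4% |

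**4. Does the term recover the loss?** Simulation of ranked data at one time point, in a subject-effects model, without and with a categorical day term: 77% v 78% at no drift, 73% v 78% at D = 1, and 56% v 77% at D = 2. Without the term, type I error was 3.6% at D = 1 and 1.1% at D = 2.

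**5. After the gate.** A day-constant shift cancels from differences between time points, so the three-way test is essentially unaffected. A separate simulation assumed 20 subjects, five time points and the non-cancelling Williams labelling. Power to pass the gate and then the peak contrast, without v with adjustment for day, was 43% v 44% at D = 0.5, 36% v 41% at D = 1 and 27% v 45% at D = 2.

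**6. Unequal orders, D = 1, 20 subjects.** In the non-cancelling labelling the four sequences have offsets of ±4/3 and ±2/3.
- Counts 4/6/6/4, worst assignment: (6 × 4/3 + 6 × 2/3 − 4 × 4/3 − 4 × 2/3)/20 = 0.20 SD. Other assignments give 0.07 or 0.
- Counts 4/8/4/4, worst assignment: 4 × (4/3)/20 = 0.27 SD. The other possibility is 4 × (2/3)/20 = 0.13.
- In the cancelling labelling the shift is 0 for both.

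So the ranges are 0 to 0.20 and 0 to 0.27 SD. Even in the worst cases, simulated type I error stayed at 4–5%.

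**7. Pre-dose subtraction.** If a day adds δ to every reading, then (y + δ) − (y₀ + δ) = y − y₀, and the drift disappears from the contrast with no day term.

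**The case against.** The SAP's general paragraph governs the later models and commits to an order test, which cannot be run without some order or day term. If a significant result led to adding day, little would be lost: in the simulation at step 5, that rule gave the same power as always including day. This stands as far as it goes, and a sponsor could choose that route. But the SAP does not say that the test changes the model, and fixing the term in advance avoids a choice made after the data are seen.

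The harm is also conditional. It needs drift of around 1 SD, an order scheme that does not cancel it, and no same-day subtraction. That is correct and is why the point is minor.

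The proposed term was checked in a simpler model than the SAP's, not in the full rank-based fit with unstructured covariance and ANOVA-type statistics; the simulation at step 5 entered day as a covariate on per-subject double differences. The design constants do not depend on this, but the exact power figures do.

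A reader might infer that the omission biases the result or produces false positives. The documents do not support that: the design is described as counterbalanced, and under balance the tests err on the cautious side. A material shift needs unequal orders, which could arise because dropouts are retained, but no dropout rate is given. A reader might also infer that the reassurance about the baseline session is wrong. It could be right, if it means a pre-dose reading that is subtracted, or it could refer to a separate visit. The text does not settle this.

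**Conclusion.** The point holds as a minor one. The only written model omits test day in a four-day crossover whose own plan expects to look for order effects. With balanced orders the consequence is lost precision in the per-time-point contrasts and simple effects, not bias. The loss is 1 to 2 points of power at 0.5 SD of total drift and roughly 5 to 8 points at 1 SD, starting from 80%. It grows quickly beyond that. The contrast loses nothing under the cancelling Williams labelling (given the unstructured covariance the SAP specifies) or under same-day subtraction.

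These sizes rest on assumed linear drift, constant within a day, and on assumed order schemes and sample size. The shifts of 0.20 and 0.27 SD under mildly unequal orders are worst cases. The missing consequence of the order test and the undefined baseline session are gaps in detail; neither would carry the point alone.

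**What to change.** Add to the SAP: *Test day (1–4) is included as a categorical fixed effect in all mixed models, including the rank-based model, whatever the result of the test for order effects.*

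The cost is wording and about 3 degrees of freedom; no new data are needed. With equal orders and no drift, power falls by less than 1 point (80.0% to 79.9% in a pooled model; 69.9% to 69.4% for the ranked contrast). With orders of 4/6/6/4 or 4/8/4/4 the pooled figure goes from 80.0% to 79.1% or 78.3%, a loss of 1 to 2 points. The cost would be higher if order were simply randomised without balance (about 2 points pooled, up to 7 in a contrast-only regression), but that is not the design described. The SAP should also say how the day term sits with the ANOVA-type statistics.

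As an accompanying clarification, say what the baseline session is (for example a pre-dose measure on each day, or a separate visit) and whether it enters the model, or delete the sentence that relies on it.

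### The only written route to a conclusion on attenuation is a 3-way interaction on ranks followed by per-time contrasts; an unconditional time-averaged contrast in rating points, with a confidence interval, should be added

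*SAP*

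**What the plan says.** The Protocol (Objective) puts the question as one of attenuation: "The main objective of this study is to evaluate whether iomazenil can attenuate the affective and cognitive effects of alcohol". The SAP paragraph on the buzzed feeling state takes up the subjective part of it.

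- **Reason for ranks:** "We expect that the behavioral data will not conform to normality as in our previous studies".
- **Method:** "The analysis will be performed by rank transforming the data, then fitting a mixed-effects model". The covariance is unstructured, P values are adjusted to the ANOVA-type statistic (ATS), and ethanol, iomazenil and time are all within-subject factors.
- **Decision path:** "If the 3-way interaction among ethanol, iomazenil, and time are significant", ethanol-by-iomazenil contrasts are run at each time point. Where such a contrast is significant, "the simple effects of ethanol, and iomazenil will be tested to determine the nature of the interaction".
- **Multiplicity:** Bonferroni within a domain but not across domains. The SAP's opening paragraph sets a two-sided 0.05 criterion that "will be used throughout to determine statistical significance".
- **Timing of ratings:** the Protocol (Research Methodology) says "Measures of intoxication will be collected before, and several times during and after drug administration".

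The SAP does not say what follows if the 3-way term is not significant, what set of observations is ranked together, or whether the pre-dose rating is a level of time. Neither document plans a difference in rating points, a rank-based effect measure, or a confidence interval.

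**The concern.** Attenuation means that iomazenil lowers the rating more when ethanol is active than when it is placebo. That is a 2-way ethanol × iomazenil contrast over the period after iomazenil is given. The written path to it has three features, each of which can cost sensitivity:

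1. **It starts from the 3-way term.** An attenuation that is steady over the modelled times produces little or no 3-way interaction.
2. **It splits the follow-up.** The evidence is divided over time points and each contrast is Bonferroni-corrected.
3. **It works on ranks.** Ranking does not preserve interactions. If scores without ethanol are bunched, pooled ranking stretches small differences among them and compresses differences among the spread-out ethanol scores, where attenuation would appear.

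The trial could therefore see ratings fall under ethanol, find the 3-way rank term non-significant, and have no planned estimate with which to describe the fall. A reader of the report could then take the result as showing no attenuation.

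**Working it through.** **No figure to reproduce.** The documents state no sample size, power, effect size or SD. From the documents come the 2×2 within-subject design with four test days, the two-sided 0.05 level, the rank/ATS method and the order of tests. Everything else below is assumed.

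**Assumed inputs.** n = 20; 5 times; ethanol raises the mean by 40 points; iomazenil lowers it by 15 points under active ethanol and by 0 under placebo ethanol. Ethanol acts at 0, 1, 1, 0.9, 0.7 of full effect over the times, and iomazenil at 0, 0, 1, 1, 0.6. Correlation is 0.7 within and 0.3 between sessions. SD without/with ethanol is 6/18, 12/18 or 18/18. Midranks are taken over all observations. Per-time contrasts use 0.05/5 = 0.01. Errors are normal, or lognormal with sigma 0.8, standardized.

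**Formulas.**
- 3-way test: F = n·m′Tm / tr(TV), with Box degrees of freedom [tr(TV)]² / tr(TVTV). Here m and V are the mean vector and covariance of the 20 session-by-time scores, and T is the projection for the 3-way term.
- Double difference for subject i: D_i = the average over post-iomazenil times of (iomazenil minus placebo under active ethanol) minus (iomazenil minus placebo under placebo ethanol).
- True D here: −15 × (1 + 1 + 0.6)/3 = −13 points.

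**Procedures compared.**
- *Planned sequence:* significant 3-way rank term, then a significant per-time contrast, then lower scores with iomazenil under ethanol.
- *One contrast:* signed-rank test on D_i in the direction of attenuation, plus lower scores with iomazenil under active ethanol, with no preceding 3-way test.

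**Success rates** (500 trials per setting; Monte Carlo SE at most √(0.25/500) = 2.2 points):

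| Errors | Procedure | SD 6/18 | 12/18 | 18/18 |
|---|---|---|---|---|
| Normal | Planned sequence, ranks | 25% | 28% | 24% |
| Normal | One contrast, ranks | 49% | 50% | 44% |
| Normal | One contrast, ratings | 84% | 70% | 57% |
| Lognormal | Planned sequence, ranks | 46% | 47% | 39% |
| Lognormal | One contrast, ratings | 87% | 81% | 68% |

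With lognormal errors, the one contrast on ranks succeeds in about 62–68% across the three settings.

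**Where the gain comes from (normal errors).** Replacing the sequence by one contrast, still on ranks, adds 49−25 = 24, 50−28 = 22 and 44−24 = 20 points. Moving from ranks to ratings then adds 84−49 = 35, 70−50 = 20 and 57−44 = 13 points. The procedure thus accounts for 24/59 = 41%, 22/42 = 52% and 20/33 = 61% of the total gain.

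**The 3-way test alone, ranks vs ratings.** Normal: 62 vs 98%, 65 vs 91%, 61 vs 77%. Lognormal: 77 vs 89%, 75 vs 80%, 70 vs 71%. The cost of ranking shrinks with skew and vanishes with skew and equal spread. The mechanism shows at SD 6/18 with normal errors: among 20 × 4 × 5 = 400 ranks, one rating point moves about 16 ranks near the no-ethanol mean but only 3 near the ethanol mean.

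**Steady attenuation.** A separate simulation used log-scale data, four post-dose times, no pre-dose level, and a median falling from 40 to 28 under ethanol at every time. At n = 20, 40 and 60 the 3-way rank test was significant in 4%, 5% and 5% of trials. The 2-way rank test was significant in 61%, 89% and 97%, and the 2-way test in points in 83%, 98% and 100%. With a pre-dose level included, and the effect fading over time, the 3-way rank test reached 10%, 18% and 27%.

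**The case against.** Ranking with ATS is a recognised response to expected non-normality and is valid for its own hypothesis about distributions. **That stands.** A reader might infer that ranking is the fault. The decomposition does not support this, since about 40 to 60% of the gain under normal errors needs no change of scale.

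A reader might also infer that the rank loss arises whatever the spread. It does so under normal errors, but not under the skew that the SAP leads one to expect. With lognormal errors and SD 18/18, a larger run gave the 3-way test 66% on ranks and 63% on ratings. Skew does not always remove the gap, however: with skew and a floor at SD 12/18 it was 72% vs 92%.

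It is also too strong to say that the plan examines attenuation only through the 3-way term, because the fitted model includes the 2-way term. What is missing is any conclusion attached to that term. Nor does the SAP say that a non-significant 3-way term means no attenuation. That is a misreading the text leaves open, not one it makes.

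The added contrast is not stronger than the 3-way rank test everywhere. At SD 18/18 with normal errors, the signed-rank test rejects in 56% against 60% for a 15-point reduction, and in 81% against 87% for 20 points. Its advantage there is over the full sequence. Finally, no passage defines attenuation in rating points. Points are a reasonable scale for the question, but choosing them is a decision the plan has still to make.

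None of this supplies an unconditional test of attenuation or an estimate with an interval.

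**Conclusion.** The point holds as a **cheap improvement**. The SAP ties the attenuation question to one written path, attaches no conclusion to the 2-way term, gives no rule for a non-significant 3-way term, and plans no estimate or CI in rating points. Those facts depend on no simulation.

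The size does. Under the assumed inputs the planned sequence succeeds in roughly a quarter of trials with normal errors and two fifths to just under a half with lognormal errors, for a reduction that one unconditional contrast in points detects in more than half to well over four fifths. Part of the loss comes from the sequence and part from ranking. The ranking part is large if no-ethanol scores are bunched, and small or absent with skewed errors and equal spread. The documents do not show which case applies.

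A reader might infer a serious risk of falsely claiming attenuation, because the 3-way rank term can be significant when effects are exactly additive in points. The later planned steps largely prevent it: the full sequence ended in an attenuation result in at most 0.6% of simulated additive settings.

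**What to change.** Keep the rank/ATS analysis and state which observations are ranked together. Add one SAP paragraph, not conditional on the 3-way term:

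1. For each subject, compute the iomazenil effect under active ethanol minus that under placebo ethanol, averaged over a stated post-iomazenil window. Report it in rating points with a 95% CI and a signed-rank test, and name it as the interaction test for attenuation.
2. Require also that ratings are lower with iomazenil under active ethanol before attenuation is claimed.
3. State that a non-significant 3-way rank term alone is not evidence of no attenuation.
4. Fit the same mixed model to the untransformed ratings as support. This retains the property the SAP values: "One of the advantages of this approach is that it uses all available data on each subject including dropouts".

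The cost is one paragraph, one derived score per subject and one extra model run, with no new data. There are two downsides. The double difference uses only subjects with all four sessions; at n = 20 its 95% CI half-width is about 8 to 12 points under these assumptions, against a true value of 13. And the two scales may disagree, in which case both must be reported. In simulated additive settings the rule made a false claim in at most 2.9%. If the data have already been analysed, label the addition post hoc.

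### The SAP's only written decision rule for the buzzed aim starts from the 3-way interaction with time; the overall ethanol × iomazenil term, which matches the aim, has no stated role

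*SAP*

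**What the plan says.** **Aim.** The SAP's analysis paragraph opens: "To determine whether iomazenil, attenuates the “buzzed” feeling state of ethanol intoxication in healthy human subjects". The Protocol's Objective ("The main objective of this study is to evaluate whether iomazenil can attenuate the affective and cognitive effects of alcohol") and its hypothesis under Research Methodology ("iomazenil, will attenuate several measures of ethanol intoxication in healthy human subjects") ask the same kind of question. None of the three states a pattern over time.

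**Model.** A rank-based mixed model with ethanol, "iomazenil (active or placebo) and time as within-subject factors". The levels of time are not listed.

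**Decision rule.** An if-then statement: "3-way interaction among ethanol, iomazenil, and time are significant, contrasts for testing interactions between iomazenil and ethanol will be performed at each time point". Simple effects follow at the time points where that contrast is significant. No other decision rule is written for this aim.

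**Levels.** The SAP's general paragraph sets two-sided 0.05 for every test. It adds: "Significance levels for secondary comparisons will be adjusted for multiple tests using the Bonferroni correction". The analysis paragraph also applies Bonferroni within domains. No comparison for this aim is called primary.

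**Timing.** Under Research Methodology: "Measures of intoxication will be collected before, and several times during and after drug administration". Ethanol is given first, "followed by placebo or active iomazenil", so readings before any drug, and readings on ethanol but before iomazenil, are both possible.

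**The concern.** In a 2×2 within-subject design, attenuation means that the ethanol effect is smaller with iomazenil than without it. That is the ethanol × iomazenil contrast. The 3-way term asks something else: whether that contrast changes over time. The written rule reaches the contrast that matches the aim, one time point at a time, only after the 3-way term is significant.

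The SAP therefore has no instruction for a trial in which the 2-way term is significant and the 3-way term is not. Whether that result meets the aim, and at 0.05 or an adjusted level, would be settled after the data are seen. The undefined levels of time add to this, because they determine what both terms measure.

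**Working it through.** **Inputs.** The documents give alpha = 0.05, two-sided. They give no sample size, effect, SD or number of time points, so there is no power figure to reproduce. Everything below other than alpha is assumed.

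**Notation.** For each subject and time, D_t = (ethanol + iomazenil) − (ethanol + placebo) − (placebo + iomazenil) + (placebo + placebo), with SD 1 and equal correlation ρ between times. The 2-way term tests the mean of D_t over all T modelled times (t test, n−1 df). The 3-way term tests differences of D_t between times (Hotelling, unstructured covariance), with noncentrality λ = n·Σ(μ_t − μ̄)²/(1 − ρ).

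**1. Steady effect of 0.5, five post-iomazenil times, n = 20, ρ = 0.5.**
- 2-way: variance of the mean = (1 + 4×0.5)/5 = 0.6; SE = √(0.6/20) = 0.173; noncentrality 0.5/0.173 = 2.89; power 78%.
- 3-way: every μ_t equals μ̄, so λ = 0 and the test rejects at 5%, its alpha.
- Over ρ = 0.3–0.7 and n = 20–30: 2-way 68–98%, 3-way 5% throughout.

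**2. The same, but one pre-drug level (effect 0) plus four post-iomazenil levels.**
- 2-way: mean falls to 0.4; 0.4/0.173 = 2.31; power 59%.
- 3-way: λ = 20×(0.4² + 4×0.1²)/0.5 = 20×0.20/0.5 = 8 on (4, 16) df; power 47%.
- Average over the four post-iomazenil times: variance (1 + 3×0.5)/4 = 0.625; SE = √(0.625/20) = 0.177; 0.5/0.177 = 2.83; power 77%.
- Over the same ranges: 2-way 50–89%, 3-way 34–92%, post-iomazenil contrast 67–97%. At ρ = 0.7 and n = 30 the 3-way test (92%) beats both the 2-way term (68%) and the contrast (85%).

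**3. Fading effect (1, 0.75, 0.5, 0.25, 0; same mean 0.5), five post-iomazenil times, n = 20, ρ = 0.5.** λ = 20×(0.25 + 0.0625 + 0 + 0.0625 + 0.25)/0.5 = 25; 3-way power 95%, against 78% for the averaged contrast.

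**4. The SAP's own scale.** Simulation on pooled ranks with the ANOVA-type statistic, complete data. Assumed: n = 20 or 30; 4–6 post-iomazenil times; a 0–100 score with baseline 0, 5 or 15; ethanol +50; iomazenil −10 under ethanol, steady; SDs 15 (subject), 12 (session), 10 (residual), with subject and session variance either under active ethanol only or in all cells.

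| Levels of time | 3-way | Overall 2-way | Contrast over post-iomazenil times | 2-way significant, 3-way not |
|---|---|---|---|---|
| Post-iomazenil only | 4–6% | 35–68% | same as 2-way | 32–66% |
| Plus a pre-drug level | 8–30% | 20–57% | 29–62% | 16–50% |
| Plus pre-drug and ethanol-only levels | 10–48% | 17–48% | 31–63% | 12–39% |

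With a linearly fading effect of the same average, the full written sequence (3-way term, Bonferroni-adjusted time-point contrast, simple effect of iomazenil under ethanol) is positive in 16–78% and the averaged contrast in 30–69%. The written sequence is ahead in 30 of 60 settings.

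**5. Error rate if either term may support the aim.** At 0.05 each and independent: 1 − 0.95² = 0.0975. The rank simulations give roughly 8–12%. Bonferroni over the two would put each at 0.05/2 = 0.025. The 2-way power across all three rows of the table would then be 10–56%, instead of 17–68% at 0.05.

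**The case against.** The strongest reply is that nothing is blocked. The factorial model tests the 2-way term anyway, the conditional sentence says only when time-point contrasts are run, and reading the lower-order interaction when the higher one is not significant is ordinary practice. This stands in part: the SAP does not forbid using the 2-way term, and a reader who infers that the plan cannot test attenuation goes beyond the text. But ordinary practice leaves two terms that could each be taken as support, with no stated priority, and that is the source of the inflated error rate.

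A reader might also infer that the 2-way term has no significance level. The general two-sided 0.05 applies to all tests, so it has a default. What is unclear is whether the Bonferroni adjustment applies as well.

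A third tempting reading is that a significant 2-way term with a non-significant 3-way term is the result to expect. That depends mainly on modelling post-iomazenil times only, which no passage confirms. With earlier levels it occurred in at most half of the simulated trials.

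Nor is the 3-way term always the weaker test. It does well when attenuation fades. With a steady 20-point effect, both earlier levels and variance in all cells, a further simulation gave it 89–99% against 58–79% for the overall 2-way term.

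**Conclusion.** The point holds as a gap in the decision rule, and closing it is a cheap improvement. Confidence is high on the text: the sole written rule starts from the 3-way term, the overall 2-way term has no stated role, the branch after a non-significant 3-way term is missing, and the levels of time are undefined.

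The power figures are illustrations only. The one result that does not depend on the assumed effect size or SDs is that perfectly steady attenuation, with only post-iomazenil times modelled, contributes nothing to the 3-way term on the scale where it is steady. In other settings the size of the loss, and sometimes its direction, depends on the time levels, the time course, the correlation and the variance pattern, none of which the documents give. Dropout was not simulated. The error rate of roughly 8–12% applies only if either term is accepted as support.

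**What to change.** In the SAP's analysis paragraph for this aim:

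1. Name one ethanol × iomazenil contrast, averaged over listed post-iomazenil time points within the planned rank-based model, as the test of the aim at two-sided 0.05, whatever the 3-way result.
2. List the levels of time, and say whether pre-drug and pre-iomazenil readings are among them or enter in another way.
3. Keep the 3-way test and the Bonferroni-adjusted time-point contrasts as labelled secondary analyses of time course.

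The cost is a few sentences and one contrast statement, with no new data. The downside is that the averaged contrast is less sensitive than the 3-way route to brief or fading attenuation. Keeping that route covers much of this: in the fading rank simulations, one or the other was positive in 42–82%. With no iomazenil effect the combination was positive in 4–7%, so the retained route should stay labelled secondary.
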